8.0 EXTENT OF EXPOSURE AND TREATMENT COMPLIANCE

8.1 EXTENT OF EXPOSURE OF STUDY TREATMENT

The number and percentage of patients who received 1 or 2 randomized IV doses will be summarized by treatment group for the Safety Population. IV administration notes including site reaction at placement of IV, reaction to adhesive, infusion interruption, failure of administration device, increase in suicidality based on clinical evaluation, and perceptual disturbance based on mental status assessment are collected. For each item, the number and percentage of patients who had a 'yes' response will be summarized by treatment group and visit for the Safety Population.

8.2 EXTENT OF EXPOSURE OF BACKGROUND ADT

The number and percentage of patients taking each qualifying ADT will be summarized by treatment group for the mITT Population. The mean daily dose for a patient over a study period is defined as the total daily dose administered by a patient during that study period as captured on the CRF, divided by the duration the patient participants in that study period, measured in days. The mean daily dose for each ADT will be summarized using descriptive statistics (number of patients, mean, SD, median, minimum, and maximum) by treatment group for the mITT Population.

8.3 TREATMENT COMPLIANCE OF BACKGROUND ADT

Dosing compliance for the background ADT during a specified period is defined as the total daily dose received by a patient during that period divided by the total daily dose prescribed during the same period as recorded in the eCRF multiplied by 100 regardless if a patient discontinued from the study. Descriptive statistics for ADT compliance will be presented for each ADT and overall by the treatment group for the randomized treatment period for the mITT Population.

8.4 WEIGHT ADJUSTED DOSE OF RAPASTINEL

The dose of rapastinel will be divided by patient baseline weight and summarized by descriptive statistics including total number of patients who received rapastinel, mean, standard deviation, minimum and maximum for the Safety Population.

9.0 EFFICACY ANALYSES

All efficacy analyses will be based on the mITT Population, unless stated otherwise. The baseline for each specific efficacy endpoint is defined as the last measurement prior to the first dose of randomized treatment. The Day 0 measure for each specific efficacy endpoint is defined as the last measurement prior to the first dose of double-blind IP in the placebo lead-in period. The analyses for the placebo lead-in period will be presented for all patients combined and separately for the placebo responders vs. non-responders using the Enrolled Population. All statistical hypothesis tests will be performed at the 2-sided 5% significance level for main effects. All confidence intervals (CIs) will be 2-sided 95% CIs, unless stated otherwise.

For efficacy analyses in which study center is a factor, a *small center* will be defined as a center with less than 2 placebo non-responder patients in at least 1 treatment group in the mITT Population. Small centers will be pooled to form pseudo-centers so that each treatment group includes at least 2 placebo non-responder patients within the center for the mITT population. Pooling will be done using the following algorithm:

Based on the number of placebo non-responder mITT patients, small centers will be ordered from the largest to the smallest, and centers of the same size will be ordered from the largest center number to the smallest center number. The pooling process starts with the largest small center from the top, which will be pooled with the smallest from the bottom until a non-small center is formed. The process will be repeated using the small centers left out after the first pass. If any centers are left out at the end of the process, they will be pooled with the smallest pseudo-center. If there is more than 1 smallest pseudo-center, the pseudo-center with the smallest center number will be selected. In case the pseudo-center formed by pooling all small centers is still a small center, it will be pooled with the smallest non-small center. If there is more than 1 smallest non-small center, the one with the smallest center number will be selected.

If any, the centers with only placebo responder patients will be ordered from largest to the smallest by the number of patients. The smallest pooled center (based on placebo non-responder as defined in the previous paragraph) will be combined with largest center with only placebo responder patients; the second smallest pooled center (based on placebo non-responder as defined in the previous paragraph) will be combined with the second largest center with only placebo responder patients; the remaining centers with only placebo responder patients will be combined similarly. Centers with same number of patients will be further ordered by the center code.

The final pooled pseudo-centers will be used for all efficacy analyses when the model is adjusted for study center.

The efficacy analyses of MADRS assessments will be based on the rater-administered MADRS. The efficacy analyses using the mITT population will be performed based on the treatment to which the patient is randomized regardless of the actual treatment received. If a patient is randomized based on an incorrect stratum, then this patient will be analyzed according to the stratum to which the patient should have been assigned per the electronic data capture system, instead of the stratum per the randomization system of IWRS.

9.1 PRIMARY EFFICACY PARAMETER

The primary efficacy parameter will be the change from baseline to Day 21 in MADRS total score for the mITT population. The MADRS total score is the sum of the 10 individual items. If more than 2 items are missing, then the total score will be set to missing. If there are multiple assessments of MADRS total score for the same nominal visit of a patient, only the last assessment will be used in the analysis.

The primary efficacy parameter will be analyzed using a mixed model for repeated measures (MMRM) with treatment group, pooled study center, visit, placebo responder status at Day 7, and treatment group-by-visit interaction as the fixed effects, and Day 0 MADRS total score, baseline MADRS total score, Day 0 MADRS total score-by-visit and baseline MADRS total score-by-visit interactions as covariates. An unstructured covariance matrix is used to model the covariance of change in scores within patients. The Kenward-Roger approximation will be used to estimate denominator degrees of freedom ([Kenward et al, 1997](#)). The analysis will be performed based on all post-randomization data using only the observed cases without imputation of missing values.

In the case that the MMRM model with unstructured covariance fails to converge with the default algorithm, then the Fisher scoring algorithm will be used to provide better initial values of the covariance parameters; if the model still does not converge, a simplified model without term for study center will be used to find the initial values of the covariance parameters. In the rare event that the model still does not converge after using those initial values, simplified covariance structures will be used to fit the model in the following order until the model converges: (1) ante-dependence, (2) heterogeneous autoregressive, (3) Toeplitz, and (4) compound symmetry.

To assess the robustness of the primary MMRM results to the possible violation of the missing-at-random assumption, a sensitivity analysis using a pattern-mixture model based on non-future dependent missing value restrictions (Kenward et al, 2003) will be performed. The pattern for the pattern-mixture model will be defined by the patient's last visit with observed value. The observed MADRS total score at a visit is assumed to have a linear relationship with the patient's prior measurements. The missing values will be imputed under the assumption that the distribution of the missing observations differs from the observed only by a shift parameter value Δ . The dataset with missing values will be analyzed using the same model as the primary analysis for between-treatment group comparisons. The imputation of missing values and the analysis will be performed multiple times and the inference of this sensitivity analysis will be based on the combined estimates using the standard multiple imputation technique. The values for Δ will be selected as 0 to 8.

[figure not shown]

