3.0 INTRODUCTION

Study RAP-MD-01 is a Phase 3, multi-center, randomized, double-blind, placebo-controlled, parallel-group study in patients who are 18 to 65 years of age, meet DSM-5 (Diagnostic and Statistical Manual of Mental Disorders, Fifth Edition) criteria for Major Depressive Disorder (MDD), have a minimum score of 25 on the Montgomery-Åsberg Depression Rating Scale (MADRS), and have an ongoing inadequate response to antidepressant therapy (ADT).

[figure not shown]
The study will consist of up to a 14-day screening and washout period followed by a 1-week placebo lead-in period, a 2-week randomized treatment period, and then a 1 week of safety follow-up period. Both the placebo lead-in period and randomized treatment period will be conducted in a double-blind (DB) manner. Consequently, the combination of these two periods is referred to as the DB treatment period.

Signed informed consent from the patient or the patient's legally authorized representative will be obtained before any study-related procedures are begun. At the end of the screening period, patients meeting the eligibility criteria for this study will be enrolled into a 1-week, double-blind, placebo lead-in period intended to identify placebo responders. Placebo responders will be defined by meeting at least 1 of the following criteria at any time point during the 1-week double-blind placebo lead-in:

[figure not shown]
- Patients with $\geq 50\%$ decrease from Day 0 MADRS total score
- Patients achieving a MADRS total score of ≤ 14 points

Upon completion of the placebo lead-in period, patients will be randomized in 1:1 ratio to receive either rapastinel 450 mg or placebo, adjunctive to ongoing ADT. Randomization will be stratified by patient's responder status (as placebo non-responder vs. placebo responder) achieved during the end of the placebo lead-in period. The schedule of visits and procedures for study RAP-MD-01 is presented in [Table 3-1](#). The study design is shown graphically in [Figure 3-1](#).

This SAP provides a more technical and detailed elaboration of the statistical analyses of efficacy and safety data as outlined and/or specified in the final study Protocol Amendment 2 (version dated 12OCT2018), Amendment 3 (version dated 07DEC2018), the Restricted Access Addendum Amendment 2 (version dated 12OCT2018), and Amendment 3 (version dated 07DEC2018). Specifications of tables, figures, and data listings are contained in a separate document.

RES

[figure not shown]

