6.0 PATIENT DISPOSITION

The number of patients in the Enrolled, Safety and mITT populations will be summarized by treatment group and by study center.

Screen-failure patients (ie, patients screened but not included in the enrolled population) and their associated reasons for failure to enroll will be tabulated overall for all screened patients.

The number and percentage of patients in the mITT population who complete the randomized treatment period, of patients who prematurely discontinue during the same period and who entered the safety follow-up period will be presented for each treatment group and pooled across treatment groups for placebo lead-in period responders and non-responders both separately and combined. The reasons for premature discontinuation during the randomized treatment period as recorded on the disposition pages of the electronic case report forms (eCRFs) will be summarized by treatment group and placebo lead-in period responder status for the mITT Population.

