9.2 KEY SECONDARY EFFICACY PARAMETERS

[figure not shown]
There are 3 key secondary efficacy parameters as listed below:

[figure not shown]
1. Change from baseline to Day 8 (1 Day after the first randomized treatment) in MADRS total score for mITT population
2. Change from baseline to Day 21 in MADRS total score for the placebo non-responders of mITT population
3. Change from baseline to Day 8 in MADRS total score for the placebo non-responders of mITT population

The key secondary parameters will be analyzed using the same MMRM model as for the primary efficacy parameter, except the placebo responder status at Day 7 will be excluded for the analyses of the 2nd and 3rd key secondary efficacy parameters listed above. A sequential testing procedure will be used to control the overall type I error rate at 5% for the comparisons of between-treatment difference of multiple secondary efficacy parameters in the order listed above. Specifically, the change from baseline to Day 8 in MADRS total score for the mITT population will be tested first at the significance level of 0.05. If the between-treatment comparison is statistically significant, then the analysis of 2nd and 3rd key efficacy parameters for the placebo non-responders will be performed at the same significance level sequentially as long as the treatment effect is statistically significant in the preceding testing.

Plots of fitted (least squares) mean values and their standard errors based on the MMRM model for the change in MADRS total score will be presented by treatment group and by visit.

REDACTED

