While the study was ongoing, the primary efficacy variable was revised to be the change from baseline in MADRS score at the last visit, Day 21, and the primary efficacy study population was revised to include all randomized patients (placebo responders and placebo non-responders) based on the feedback by the FDA, EMA, and PDMA. Both of these changes were included in Amendment 2 of the protocol. At the same time of Amendment 2, a blinded data review was conducted for Studies RAP-MD-01, RAP-MD-02, and RAP-MD-03. The pooled SD for the three studies were 7.4, 8.0, and 8.7, respectively, all smaller than the originally assumed 10 points. Sample size was re-calculated using 8.7 as the common SD. The calculation used MMRM model with simulations; it also assumed correlation of 0.5 between the repeated measures and a common drop-out rate of 10% during the randomized treatment period and an additional 5% drop-out rate during the placebo lead-in period for all treatment groups. To have 90% power, the total sample size required is 360 patients. However, the study had already enrolled more than 440 patients with less than 5% of overall drop-out rate, surpassing the re-estimated sample size of 360 patients. The study enrollment was halted as soon as operationally feasible. The final sample size is approximately 460 patients (230 patients per treatment group).

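### Does the loose timing of placebo-responder status (any time in the lead-in, its end, or Day 7) put the model covariate and the non-responder subgroup on different rules?

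*SAP*

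**What the plan says.** SAP 3.0 holds the only definition. A placebo responder has a fall of at least 50% from the Day 0 MADRS total, or a total of 14 or less, "at any time point during the 1-week double-blind placebo lead-in". Later in the same section, randomization is stratified by the status "achieved during the end of the placebo lead-in period".

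The term is then used as follows:

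- SAP 9.1 (primary MMRM) lists "placebo responder status at Day 7" as a fixed effect. Day 0 MADRS, baseline MADRS and their interactions with visit are also in the model.
- SAP 9.2 keeps that model for the key secondary parameters, "except the placebo responder status at Day 7 will be excluded" for the second and third. Those two are restricted to placebo non-responders, and no timing is attached to that word.
- SAP 6.0 tabulates discontinuation reasons by "treatment group and placebo lead-in period responder status for the mITT Population".
- SAP 9.0 pools small centers by non-responder count: "Based on the number of placebo non-responder mITT patients, small centers will be ordered from the largest to the smallest".
- SAP 9.0 also moves a wrongly stratified patient to the stratum to which he or she "should have been assigned per the electronic data capture system, instead of the stratum per the randomization system of IWRS".

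Protocol 9.2 has efficacy assessed at every visit, so Day 1 and Day 4 scores exist and a transient response can be seen.

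**The concern.** Read literally, these phrases describe two different variables. One is cumulative: a responder at Day 1, 4 or 7. The other uses the Day 7 score only. SAP 15.1 encourages the second reading, because its Table 15.1-1 treats Day 7 as a separate analysis visit from Day 1 and Day 4.

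The two rules can differ in one direction only. Every Day 7 responder is also an any-time responder, so the patients at issue are those who respond at Day 1 or Day 4 and lose the response by Day 7. If the covariate followed the Day 7 score while the stratum, subgroup and pooling followed SAP 3.0, these patients would be coded inconsistently within one analysis. The status also decides who enters the second and third key secondary analyses, which belong to the alpha-controlled sequence. It affects the pooled-center term of the primary model as well. A reader may fairly ask whether two programmers would build the same dataset from this text.

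**Working it through.** **1. Which reading does the text support?**

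- SAP 3.0 states a definition. The other places use the defined term without redefining it.
- The stratification sentence follows that definition in the same section. The end of the lead-in is when a cumulative status becomes final and randomization takes place.
- SAP 13.0, describing the original primary population, speaks of non-response during the lead-in before randomization, which is a period-based status.
- The SAP 2.0 entry for Section 9.0 says the mis-stratification rule governs the stratum effect in the model. Responder status is the only stratification factor stated in SAP 3.0, and it is the only such term in the 9.1 model. The covariate is therefore the stratum.
- In SAP 15.1, Day 7 is the date of the first randomized dose (IndexA). Table 15.1-2, which serves the change-from-baseline analyses, labels that row Baseline. Status at Day 7 is then the status as it stands at randomization.
- A Day-7-only status would be a threshold function of Day 0 and baseline MADRS, both already in the model. It would add little as a separate term.

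Under this reading, discordance is 0 of 460.

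**2. How many patients could differ under the other reading?**

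The documents give no responder rate and no lead-in mean change, so there is no stated figure to reproduce. The SD is borrowed from the sample-size calculation in SAP 13.0, which does reproduce. With SD 8.7, a difference of 3.25 (stated there for the original design), two-sided 0.05 and 90% power:

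n per arm = 2 × (1.960 + 1.282)² × 8.7² / 3.25² = 2 × 10.51 × 75.69 / 10.56 ≈ 150.6, so 151, or 302 in total. Then 302 / 0.85 ≈ 356, or 302 / (0.90 × 0.95) ≈ 353. The plan's simulated figure is 360.

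The discordant count is

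D = 460 × [P(responder at Day 1, 4 or 7) − P(responder at Day 7)].

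Inputs from the SAP: N of about 460, entry MADRS of at least 25, the two response criteria, SDs of 7.4 and 8.7, and for the correlation "it also assumed correlation of 0.5 between the repeated measures" (SAP 13.0). Assumed inputs: Day 0 mean 32 and SD 4, truncated at 25; normal changes; the mean changes shown below; and SDs of 6 and 10 and correlations up to 0.9 as extremes. The probabilities come from simulation. D was computed from unrounded values.

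| Mean change at Days 1/4/7 | SD | Correlation | P(any) | P(Day 7) | D |
|---|---|---|---|---|---|
| −3/−4/−5 | 6 | 0.9 | 0.056 | 0.045 | 5 (lowest) |
| −3/−4/−5 | 8.7 | 0.5 | 0.206 | 0.114 | 42 |
| −5/−6/−7 | 7.4 | 0.5 | 0.222 | 0.127 | 44 |
| −5/−6/−7 | 8.7 | 0.5 | 0.285 | 0.164 | 56 |
| −7/−8/−9 | 8.7 | 0.5 | 0.376 | 0.226 | 69 |
| −10/−10/−10 | 8.7 | 0.5 | 0.469 | 0.259 | 96 |
| −10/−10/−10 | 10 | 0.5 | 0.506 | 0.286 | 101 (highest) |

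For example, 460 × (0.285 − 0.164) ≈ 56. The full range is 5/460 = 1% to 101/460 = 22%. That width reflects the assumptions. Even the SDs are borrowed: 8.7 was the figure for RAP-MD-03 (7.4 for this study), and neither is given as an SD of lead-in change.

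**3. What would a mismatch do to the results?**

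Both versions of the status use only scores taken before the first randomized dose, so neither can be affected by treatment. The primary population is the whole mITT Population under either version. A coarser or finer pre-dose covariate can change precision slightly, but the test keeps its 5% level. For the second and third key secondaries the term is dropped from the model, so a mismatch confined to the covariate has no direct effect on them. Their membership and the pooling counts rest on the word non-responder, which carries no Day 7 qualifier.

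**The case for a change.** The best counter-argument is that nothing in the SAP expressly rules out the Day 7 reading. Dropping the term in SAP 9.2 fits both readings: any-time non-responders are all Day 7 non-responders, so the term is constant in that subgroup either way. The EDC correction in SAP 9.0 needs a rule in order to work. If the randomization system had used the Day 7 score, a programmer applying SAP 3.0 would relabel every transient responder as mis-stratified. If the subgroup itself were built on the Day 7 score, membership of two alpha-controlled tests would change.

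Part of this stands. The wording is loose, and the supplied documents cannot show which rule the randomization system used. SAP 2.0 traces the responder definition to a protocol addendum amendment that is not among them. The rest does not carry the point. Building the subgroup on the Day 7 score would mean setting aside the only definition in favor of a phrase that SAP 9.2 attaches to a model term alone. Relabeling under SAP 3.0 would still use pre-dose data only, so it would not compromise the treatment comparison. Each subgroup test would hold its 5% level under either membership rule.

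**Conclusion.** No change is called for. The timing phrases differ, but one definition governs them. Read together, they describe a single cumulative status that is complete at randomization and serves as stratum, covariate, subgroup and pooling count. On that reading no patient is classed in two ways. The alternative reading would recode roughly 5 to 101 of 460 patients for the covariate, a range set by assumed lead-in response and not by anything in the documents. Even then, no bias, loss of type I error control or effect on a stated result has been shown.

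The conclusion rests on two things: SAP 3.0 is the operative definition, and status is derived only from scores before the first randomized dose. The first is the natural reading, though it is not confirmed by the unseen addendum. The second holds under every reading. Any further wording would only record the rule already used at randomization.

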For efficacy analyses in which study center is a factor, a small center will be defined as a center with ≤ 2 patients in ≥ 1 treatment group in the mITT Population. Small centers will be pooled to form pseudo-centers so that each treatment group includes ≥ 2 mITT patients within the center. Details of the pooling algorithm will be provided in the Statistical Analysis Plan (SAP).

9.7.5.1 **Primary Efficacy Parameter**

The primary efficacy parameter will be the change from baseline in MADRS total score at end of study. The primary analysis will be performed using a mixed-effects model for repeated measures (MMRM) with treatment group, pooled study center, visit and randomized treatmentby-visit interaction as the fixed effects, and baseline MARDS total score and baseline MADRS total score-by-visit interaction as covariates. An unstructured covariance matrix will be used to model the covariance of within-patient scores. The Kenward-Roger approximation will be used to estimate the denominator degrees of freedom (Kenward et al, 1997; Kenward et al, 2003). The treatment difference for rapastinel versus placebo will be estimated and reported along with the corresponding 95% CI and nominal p-value.

In the case that the MMRM model with unstructured covariance fails to converge with the default algorithm, then the Fisher scoring algorithm will be used to provide better initial values of the covariance parameters; if the model still does not converge, a simplified model without term for study center will be used to find the initial values of the covariance parameters. In the rare event that the model still does not converge after using those initial values, simplified covariance structures will be used to fit the model in the following order: (1) ante-dependence,

[figure not shown]
- (2) heterogeneous autoregressive,
- (3) Toeplitz, and (4) compound symmetry.

[figure not shown]

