12.0 INTERIM ANALYSIS

At the time of preparation for the Protocol Addendum Amendment 2, a blinded interim analysis was performed as part of data quality review as the study was progressing. In this review, it was observed that the standard deviation for the primary and secondary endpoints were substantially lower than the originally assumed values for sample size calculations. The observed standard deviations in the blinded reviews of this study and other ongoing acute studies at the same time (RAP-MD-02, and RAP-MD-03) were taken into considerations for revising the sample size estimation in next section (Determination of Sample Size).

13.0

DETERMINATION OF SAMPLE SIZE

The originally proposed primary efficacy variable is the change from baseline (ie., Day 7) at Day 8 in MADRS total score and the primary analysis population included the subset of patients who were placebo non-responders during the placebo lead-in period before randomization. Based on that the study was planned to randomize 700 patients (including both placebo responders and placebo non-responders), assuming standard deviation (SD) of 10 points, which provides 99% power to detect a difference of 3.25 points in MADRS total score between rapastinel 450 mg and placebo at a 2-sided significance level of 0.05.

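### Fallback steps 3 and 4 of the primary MMRM (Toeplitz, compound symmetry) assume one variance for all visits; if variance grows to Day 21 and those steps are reached, the Day 21 standard error is too small

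*SAP*

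**What the plan says.** The primary analysis (SAP 9.1; Protocol 9.7.5.1) is an MMRM with an unstructured covariance matrix and Kenward-Roger degrees of freedom. If it does not converge, the plan first tries Fisher scoring for better starting values, then starting values from a model without study center. Only if that also fails does the SAP state that "simplified covariance structures will be used to fit the model in the following order until the model converges". The Protocol has "simplified covariance structures will be used to fit the model in the following order" and the same four structures:

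1. ante-dependence
2. heterogeneous autoregressive
3. Toeplitz
4. compound symmetry

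Only the autoregressive structure is labelled heterogeneous. No empirical (sandwich) variance is named at any step.

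SAP 9.0 sets the level: "All statistical hypothesis tests will be performed at the 2-sided 5% significance level for main effects". SAP 9.2 uses the same MMRM for the key secondary endpoints, except that responder status is left out for the two in placebo non-responders. SAP Table 15.1–2 gives six post-baseline visits in the double-blind period: Days 8, 11, 14, 15, 18 and 21.

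**The concern.** The primary test is a contrast at one visit, the last. Ante-dependence and heterogeneous autoregressive let each visit have its own variance, so the Day 21 standard error reflects the Day 21 spread. Toeplitz and compound symmetry, in their ordinary form, do not: the Day 21 standard error then comes essentially from the variance averaged over the six visits. Kenward-Roger corrects model-based inference for small samples but does not repair a wrong covariance structure.

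Day 8 is one day after the first randomized dose and Day 21 two weeks after it, so growth in the variance of change is plausible. Under growth, the Day 21 interval would be too narrow and the primary test would exceed its 5% level. The Day 8 standard error, used for the first key secondary endpoint, would be too large and would cost power.

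**Working it through.** **Inputs from the documents**
- Two-sided 5% level (SAP 9.0).
- About 230 patients per group, randomized 1:1; overall dropout so far under 5% (SAP 13.0, SAP 3.0).
- Blinded SDs (SAP 13.0): "The pooled SD for the three studies were 7.4, 8.0, and 8.7, respectively", in the order RAP-MD-01, -02, -03. This study's value is 7.4.
- Planning SD (SAP 13.0): "Sample size was re-calculated using 8.7 as the common SD".
- Planning correlation (SAP 13.0): "it also assumed correlation of 0.5 between the repeated measures".

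**Assumed, because the documents do not give it:** the SD at each visit. The Day 8 SD is set at 6 or 7, the Day 21 SD at 7.4 or 8.7, with a linear rise over days since baseline (1, 4, 7, 8, 11, 14).

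**The plan's own figure.** SAP 13.0 states: "To have 90% power, the total sample size required is 360 patients". The difference to "detect a difference of 3.25 points in MADRS total score between rapastinel 450 mg and placebo" is stated for the 700-patient calculation and is assumed to carry over.
- Per group: 2 × (1.960 + 1.282)² × 8.7² / 3.25² = 150.6, so 151.
- With 15% dropout: 151 / 0.85 = 177.6, so 178 per group and 356 in total, against 360 stated.
- With 360 × 0.85 / 2 = 153 evaluable per group, power is 90.4%.

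The sample size reproduces and does not depend on the fallback rule.

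**Effect of a common variance at Day 21.** With complete data and compound symmetry:
- True SE = SD(Day 21) × √(2/230).
- Model SE = √(mean of the six visit variances) × √(2/230).
- Type I error = 2 × [1 − Φ(1.96 × model SE / true SE)].

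| SD Day 8 → Day 21 | Visit SDs | √(mean variance) | SE ratio | Type I error |
|---|---|---|---|---|
| 7 → 7.4 | 7.00, 7.09, 7.18, 7.22, 7.31, 7.40 | 7.20 | 0.973 | 5.6% |
| 6 → 7.4 | 6.00, 6.32, 6.65, 6.75, 7.08, 7.40 | 6.72 | 0.908 | 7.5% |
| 7 → 8.7 | 7.00, 7.39, 7.78, 7.92, 8.31, 8.70 | 7.87 | 0.905 | 7.6% |
| 6 → 8.7 | 6.00, 6.62, 7.25, 7.45, 8.08, 8.70 | 7.40 | 0.851 | 9.5% |

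At Day 8 the same rule overstates the standard error, by a factor from 7.20/7 = 1.03 to 7.40/6 = 1.23.

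**Wider range** (Day 21 SD 8.7, correlation 0.5, complete data, true Day 21 SE 0.811):

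| Day 8 / Day 21 SD ratio | Compound symmetry SE | Type I error | Simulated (10,000 runs) |
|---|---|---|---|
| 1.0 | 0.811 | 5.0% | 4.9% |
| 0.9 | 0.771 | 6.3% | not run |
| 0.8 | 0.732 | 7.7% | 8.0% |
| 0.7 | 0.694 | 9.4% | 9.4% |
| 0.6 | 0.658 | 11.2% | 10.9% |
| 0.5 | 0.623 | 13.2% | 12.9% |

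Toeplitz gives nearly the same values. Dropout of 15%, taken as completely at random, makes little difference: at ratio 0.7 the type I error is 9.7% for compound symmetry and 9.6% for Toeplitz. In the simulation, using the Day 21 variance itself, as an unstructured fit does, gave 4.9–5.3%.

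**Structures with visit-specific variances** (5% dropout, all SD ratios tried, correlation either constant at 0.5 or decaying with time):
- Ante-dependence: about 5.0%.
- Heterogeneous autoregressive: 4.5–5.0%.
- Heterogeneous Toeplitz: 5.0% with constant and 4.5% with decaying correlation.
- Heterogeneous compound symmetry: 5.0% with constant and 3.9% with decaying correlation.

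The problem is therefore confined to steps 3 and 4, and allowing the variance to differ by visit removes it.

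**The case against.** The strongest objection is reach. Steps 3 and 4 apply only after five failures in sequence: the default unstructured fit, Fisher scoring, starting values from the model without center, ante-dependence, and heterogeneous autoregressive. The SAP itself treats even the start of the list as rare, and it already puts the two heterogeneous structures first. This stands, and it is why the point is low priority.

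The second objection is that nothing in the documents shows variance growing. The only planning SDs tied to an endpoint run the other way: 10 for the change one day after dosing, 8.7 in the re-calculation for Day 21. They were set at different times, and the blinded review found the 10 too high, so they do not show falling variance either. A reader might infer from the fallback list that the primary test is anti-conservative. The documents do not support that: the direction depends on an unreported variance pattern, and the rule matters only if it is reached.

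Third, the size depends on which SD is used. The 8.7 is RAP-MD-03's pooled value, adopted for planning; with this study's 7.4 the inflation is smaller. What matters is also the residual SD after adjustment for baseline and Day 0 score by visit, center and responder status, which is not reported.

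Fourth, Toeplitz might have been programmed as heterogeneous. The SAP's history of changes says SAS code was moved to a separate document, but that note is in the entry for the pattern-mixture appendix and does not settle how the primary model is coded.

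**Conclusion.** The point holds conditionally. On a plain reading, steps 3 and 4 give a wrong Day 21 standard error whenever the variance differs by visit. Under the assumed linear growth from a Day 8 SD of 6–7, the type I error is about 5.6–7.5% if the Day 21 SD is 7.4, and about 8–10% if it is 8.7. It is 5.0% under flat variance, and the test is conservative if variance falls.

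There is no effect if the unstructured model or either of the first two fallbacks converges, as is likely with about 460 patients, six visits and under 5% dropout. A reader might extend this to a flaw in the main analysis or in the sample size. Neither follows: the unstructured MMRM and steps 1 and 2 hold the level or are slightly conservative, and the 360 reproduces independently of this rule.

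**What to change.** In SAP 9.1, mirrored in Protocol 9.7.5.1, do one of the following:

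- **Preferred:** name heterogeneous Toeplitz at step 3 and heterogeneous compound symmetry at step 4, keeping Kenward-Roger. With six visits this means 6 variances + 5 correlations = 11 parameters instead of 6, and 6 + 1 = 7 instead of 2. The cost is five extra parameters at each step, so these steps are somewhat harder to fit than the present ones.
- **Alternative:** keep Toeplitz and compound symmetry, but state that at steps 3 and 4 only, the standard error is the empirical (sandwich) one with a named degrees-of-freedom method. The cost is the loss of Kenward-Roger at those two steps.

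The sandwich should not extend to steps 1 and 2, where it would displace Kenward-Roger although the level is already held. Nor should the list stop after step 2, since that leaves no pre-specified model if both fail. If a heterogeneous Toeplitz was intended all along, saying so settles step 3. The change is one line in each document and should be made before unblinding.
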